6.1 The main efficacy indicators

Operation time (min)

Postoperative hospital stay (d) (first day after surgery to discharge day, up to 4 weeks)

Postoperative knee function Rasmussen score changes (1, 2, 3, 4, 6, 12 months)

6.2 secondary efficacy indicators

Intraoperative bleeding (ml)

Postoperative pain score (visual analogue scale (VAS)) (first postoperative day to discharge day, maximum 2 weeks)

Postoperative fracture healing time (m) (discharged to fracture healing, maximum 1 year)

Postoperative knee gap width (mm)

Postoperative articular surface maximum collapse height (mm)

Height of well-resumed postoperative articular area as a percentage of collapse area (%)

7. Safety evaluation

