[figure not shown]
Research topics	Arthroscopic Assisted Balloon Tibioplasty for the Treatment of Schatzker II-IV Tibial Plateau Fractures
purpose	Objective to compare the clinical diagnosis and treatment of open reduction and internal fixation with Schatzker II-IV tibial plateau fracture or arthroscopic assisted balloon tibioplasty of tibial plateau fractures.
overall design	This study used a randomized controlled trial design research.
diagnostic criteria	At least 2 fixed researchers by X-ray or CT examination to determine fracture type
Screening criteria	
Inclusion criteria: The following criteria must be according with.
 
(1) fresh closed fracture, X-ray and CT examination diagnosed Schatzker type II-IV tibial plateau fracture patients(2) sign the informed consent form(3) age from 18 to 80 years 
Exclusion criteria:
 
(1) exclude open fractures, pathological fractures, immunodeficiency, hematological diseases and severe hepatorenal disorders(2) refuse to sign informed consent form

Methods	
Experimental group: patients were randomly divided into the experimental group and underwent Arthroscopic Assisted Balloon Tibioplasty.
 
Control group: patients were randomly divided into control group and underwent Open Reduction and Internal Fixation(ORIF).

Curative effect observation index	
Primary Outcome Measure:
 
1.Rasmussen scores change after surgery the knee joint Rasmussen scores change after surgery [Time Frame: 1、2、3、4、6、12mouth Rasmussen scores change after surgery]
 
Secondary Outcome Measures:
 
1.Intraoperative blood loss blood loss in surgery [Time Frame: Operation day]
 
2.Postoperative pain score Postoperative pain score(Visual Analogue score, range of scores from 0 to 10, the score is designed to measure the level of the pain and the higher score is, the more painful the patient is) [Time Frame: from operation day to leave hospital day(up to 2 weeks)]
 
3.Fracture healing time Fracture healing time [Time Frame: from leave hospital day to healing time(up to 1 year)]
 
4.The percentage of joint area recovered after operation was

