	
satisfactory
 
The percentage of joint area recovered after operation was satisfactory
 
[Time Frame: 1、2、3、4、6、12 mouth after surgery]
 
5.operation time
 
Duration of surgery
 
[Time Frame: Operation day]
 
6.the postoperative hospital stay days
 
the total hospital stay days after surgery
 
[Time Frame: from operation day to Leave hospital day(up to 4 weeks)]

Safety observation index	Intraoperative vital signs, Intraoperative C arm examination, postoperative examination etc.
Visiting point	Screening / baseline: admission to the preoperative / postoperative day from the first day to the day of discharge. 1、2、3、4、6、12 mouths after the operation.
statistical analysis	Spss22.0 software was used for statistical analysis. The measurement data in SX, using t test, count data expressed as a percentage, using X - test, $P < 0.05$, the difference has statistical significance, and draw the relevant charts with RevMan software. Case characteristics and efficacy analysis were analyzed by complete analysis set (FAS) and compliance program set (PPS), and safety evaluation was analyzed by safety set (SS).
sample size	A total of 40 patients were included this project, the experimental group 20 cases and the control group 20 cases.
Research cycle	July 2017 ~ June 2020

Technology Roadmap

Technology Roadmap

Project text

1. Research topics

Arthroscopic Assisted Balloon Tibioplasty for the Treatment of Schatzker II-IV Tibial Plateau Fractures

2. Research background

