5.2 Screening period (from admission to day before surgery)

- 1) come to our hospital after injury, meet the inclusion criteria.
- 2) at least 2 permanent investigators confirm the type of fracture by X-ray or CT examination.
- 3) after signed the informed consent form, according to random table method, the patients were randomly divided into experimental group or control group for corresponding treatment.

5.3 During the study period (from the day of surgery to 1 years after surgery)

- 1) the day of surgery recorded in detail the surgical procedures, operation time, intraoperative blood loss were recorded.
- 2) from operation day to leave hospital day(up to 2 weeks),the postoperative pain score, postoperative knee gap width, postoperative hospital stay days were recorded.
- 3) the patients were followed up after leave hospital: make a detailed record of the knee joint Rasmussen scores change after surgery (Rasmussen score) (1,2,3,4,6,12 months after surgery), The

percentage of joint area recovered after operation where was satisfactory, postoperative fracture healing time, maximal postoperative articular surface collapse height, postoperative failure rate and related complications.

5.4 The end of the study period (the end of the follow-up to the project end)

1. sort the appropriate information, through epidemiological or statistical experts guidance, experimental group and control group data analysis, using SPSS 22.0 statistical software analysis, measurement data to sx, using t test, counting data Percentage, using χ^2 test, $P <0.05$ for the difference was statistically significant, and use RevMan software to draw the relevant charts.
2. based on the data and charts after treatment, organize clinical discussions and experience of relevant personnel: 1.the actual operation of the new technology found in all aspects of the existing shortcomings and explore ways to improve the arthroscopic balloon dilatation tibial angioplasty, and improve the clinical diagnosis and treatment of fractures related to our hospital level. 2 through get the follow-up data under this new technology to enrich our hospital clinical data resources.

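### The abstract names one primary outcome and section 6.1 names three, no Rasmussen comparison is designated as decisive, and the visit schedule has no Rasmussen row

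*Combined protocol and SAP*

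**What the plan says.** The project abstract has a single entry under its primary outcome heading: "1.Rasmussen scores change after surgery the knee joint Rasmussen scores change after surgery", with six time frames from 1 to 12 months. Its secondary list includes "5.operation time" and "6.the postoperative hospital stay days".

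Section 6.1 gives three main efficacy indicators of equal standing: "Operation time (min", "Postoperative hospital stay (d) (first day after surgery to discharge day, up to 4 weeks" and "Postoperative knee function Rasmussen score changes (1, 2, 3, 4, 6, 12 months". Section 6.2 then lists the secondary indicators, among them "Postoperative articular surface maximum collapse height (mm".

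The testing rule is the same in the abstract, section 5.4 and section 8.2: a t test for measurement data, a chi-square-type test for counts, and significance at P below 0.05. Section 8.1 adds that the last measured value stands in as end-point data when observation is incomplete. Section 3.3 gives 20 patients per group without a calculation. Sections 5.1 and 5.3 say that Rasmussen scores will be recorded. The visit schedule in Appendix I has an HSS row, ticked from the postoperative stay onwards, and no Rasmussen row.

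**The concern.** A plan should let a reader say, before any data exist, which single result will decide the trial or how several results will be combined. Here the answer depends on the page. A reader of the abstract would judge the trial on Rasmussen alone. A reader of 6.1 could also judge it on operation time or stay.

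The stated purpose (sections 3.1, 3.2 and 5.4) is to compare reduction of the joint surface and recovery of joint function. Operation time and stay measure neither. The two arms undergo different operations, so real differences in these two outcomes are possible. Under 6.1, one of them could carry the efficacy conclusion while Rasmussen shows nothing. Section 5.4 says the results are meant to inform treatment guidelines, so the label matters. This part of the argument needs no error-rate calculation.

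**Working it through.** **1. The lists side by side**

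| Outcome | Abstract | Sections 6.1 and 6.2 |
|---|---|---|
| Rasmussen change, six visits | Primary | Main |
| Operation time | Secondary (no. 5) | Main |
| Postoperative stay | Secondary (no. 6) | Main |
| Percentage of joint area restored | Secondary | Secondary |
| Maximum collapse height | Not listed | Secondary |
| Knee gap width | Not listed | Secondary |

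The abstract is not a shortened form of 6.1, because it names operation time and stay and classes them differently.

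**2. Does any other text settle it?**

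- *Visit:* the abstract, 5.3 and 6.1 all give six Rasmussen visits, and none is singled out.
- *Change:* no reference value is stated. Neither 5.3 nor Appendix I schedules a preoperative knee score.
- *Test:* a t test is named, but not which t test decides. There is no hierarchy, co-primary rule or adjustment.
- *Last-value rule (8.1):* it names neither a visit nor a primary outcome.
- *Sample size (3.3):* 40 patients with no effect size, SD or power. The figure cannot be reproduced and does not show which outcome the trial was planned on.
- *Schedule (Appendix I):* the one measure that both lists share has no row.

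**3. What the open choice could cost (illustration only)**

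From the documents: 20 per arm, a t test, a 0.05 threshold, three indicators and six visits. Assumed: two-sided tests (sidedness is not stated), normal data, no true difference on any outcome, each comparison tested separately, any one significant result counting, and all correlations.

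For k independent tests, P(at least one significant) = 1 − 0.95^k.

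- One test: 5%.
- Three tests (operation time, stay, Rasmussen once): 1 − 0.857 = 14.3%.
- Eight tests (operation time, stay, six Rasmussen visits): 1 − 0.663 = 33.7%. Repeated scores in the same patients are not independent, so this figure is not credible as an estimate.

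Simulation with correlated outcomes (100,000 trials per setting, 38 degrees of freedom, Monte Carlo error about ±0.3 points):

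| Tests | Assumed correlations | At least one P<0.05 |
|---|---|---|
| Three | Cross-outcome 0 to 0.5 | 14.2% down to 12.6% |
| Six Rasmussen visits | Between-visit 0.5 to 0.9, equal or serial | 11.1% to 23.7% |
| All eight | Between-visit 0.5 to 0.9, cross-outcome 0 to 0.5 | 17.3% to 31.2% |

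If every main indicator had to be significant, the error rate would not exceed 5%.

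**4. When operation time or stay truly differs**

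A significant result there is then not a false positive; the problem is what it is called. Power of one two-sided t test comes from the noncentral t distribution with noncentrality d × √(20/2) = 3.162d and 38 degrees of freedom:

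- d = 0.5 SD: 33.8%
- d = 0.8 SD: 69.3%
- d = 1.0 SD: 86.9%

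The values of d are assumptions. These are chances of a significant difference on that one outcome, whatever Rasmussen shows. They are not chances of a result that favours the balloon technique.

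**The case against.** Rasmussen is in both lists, so 6.1 adds outcomes and does not replace the abstract's choice. The last-value rule can be read as pointing to one end-point comparison. The study is small, is run in one department, and has improvement of the technique among its aims. Each of these has some weight. None of them says whether operation time or stay may carry the conclusion, and the guideline aim in 5.4 limits an exploratory-study defence. A looser translation of *main* is also hard to accept, because 6.1 is set directly against a secondary list in 6.2.

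The error rates depend on rules that the plan does not state, and they should not decide how serious the point is.

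A reader might also infer more than the text supports:

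- *That the plan tests every visit and lets any one result win, so the true error rate is about a third.* The plan states neither rule.
- *That the primary outcome was chosen after the data were seen.* The documents leave room for this; they do not show it.
- *That the balloon operation is expected to be quicker.* Section 2 describes its surgical trauma as small, which may bear on stay. It gives no basis for a difference in operation time in either direction, and it also calls the technique immature.

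**Conclusion.** The point holds as a contradiction in the current text together with an omission. Two primary lists conflict. No text fixes the governing list, the decisive Rasmussen visit, the reference for change, or a success or multiplicity rule. The score common to both lists is missing from the visit schedule. As written, 6.1 allows a difference in operation time or stay to be the main efficacy result without any difference in joint function.

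This conclusion rests on the wording alone. The size of any error inflation is conditional: it runs from none, if all indicators must succeed, to roughly 17–31% for eight separate tests under an any-one rule and the assumed correlations. The matter needs to be settled before data are examined, because a later analysis cannot supply a primary comparison that was never fixed.

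**What to change.** - **One primary outcome.** Make the abstract and 6.1 agree. Rasmussen is in both lists and fits the joint-function purpose, so operation time and stay would move to 6.2. Say openly that the measures of joint-surface reduction are secondary, although reduction is also a stated purpose.
- **One comparison.** Before data are examined, name a single primary test on the postoperative Rasmussen scores that 5.3 already plans, for example the between-group difference at 12 months or one longitudinal test. With no preoperative score scheduled, defining change from a preoperative value would need new data. Test once at two-sided 0.05, and report other visits and outcomes as secondary with confidence intervals.
- **Schedule.** Reconcile the Rasmussen score in 5.3 and 6.1 with the HSS row in Appendix I.
- **Secondary lists.** Add collapse height and knee gap width to the abstract or explain the difference. Align the recording window for stay, which is up to 2 weeks in 5.3 and up to 4 weeks in the abstract and 6.1.

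Alternatively, keep several main indicators and state a success rule and a multiplicity procedure. Under an any-one rule, Bonferroni would give 0.05/3 = 0.0167 per test for three tests, or 0.05/8 = 0.00625 for eight. At an assumed difference of 0.8 SD, power per test would fall from 69.3% to 51.6% or 37.1%.

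The cost of the preferred route is a wording amendment under section 10, signed by the principal investigator and submitted to the ethics committee. The downside is that an isolated difference at an early visit, in stay or in operation time could no longer be called the main result.

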4.3 Exit criteria

The patients were lost, half-way to quit and other unpredictable problems

5. Project design

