balloon dilatation, select the appropriate balloon needle angle, guided by fluoroscopy, placed in the center of the balloon platform collapse, so that it is in the best position, filling device of bone cement injected with bone cement after expansion, at the same time the use of arthroscopy intervention on the articular surface, prevent the reduction of the articular surface is not complete, not smooth or excessive. Then Insert the other screws, suture the incision. If the tibial plateau does not splitting, the procedure should be carried out directly, and the collapsed articular surface of the tibial plateau can be restored directly.(step 2). A detailed record of 20 case of the operation time (min), the amount of bleeding(ml), postoperative pain score (visual analogue score (VAS)), the postoperative knee joint space width (mm), hospitalization time after operation (d), fracture healing time after operation (m), postoperative maximum articular surface collapse height (mm), the percentage of the restoration of joint collapse area (%),the knee joint Rasmussen scores change after surgery (Rasmussen score), failure rate and complications.

4) Control group: under the condition of random grouping, the patients in the control group were treated with traditional Open Reduction and Internal Fixation of the tibial plateau fracture. A detailed record of 20 case of the operation time (min), the amount of bleeding(ml), postoperative pain score (visual analogue score (VAS)), the postoperative knee joint space width (mm), hospitalization time after operation (d), fracture healing time after operation (m), postoperative maximum articular surface collapse height (mm), the percentage of the restoration of joint collapse area (%),the knee joint Rasmussen scores change after surgery (Rasmussen score), failure rate and complications.

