8.1 Data selection for statistical analysis

Totally analyzed data sets (FAS): all randomized, grouped, and postoperative studies were performed with a complete analysis set. For the therapeutic data that failed to be observed in all treatments, the final measured efficacy data was used as end point data for analysis.

PPS (PPS): contained in the FAS, met the inclusion criteria, does not meet the exclusion criteria, no major protocol violations, and has completed the treatment period of efficacy evaluation, good compliance cases, this study constitutes with the scheme set.

Safety analysis data set (SS): all patients who were randomized to receive research methods and had postoperative safety evaluation data constituted the safety analysis data set of this study.

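### Fracture healing time is an event time cut off at 1 year, but the plan's t test and last-value rule give no valid value for patients lost before healing or unhealed at month 12

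*Combined protocol and SAP*

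**What the plan says.** - **Outcome.** Section 6.2 lists "Postoperative fracture healing time (m) (discharged to fracture healing, maximum 1 year"). The Project abstract gives the same window: "Time Frame: from leave hospital day to healing time(up to 1 year"). Section 5.1 records it in both arms as "fracture healing time after operation (m"). No criterion for healing is stated.
- **Test.** The Project abstract says "The measurement data in SX, using t test", and sections 5.4 and 8.2 say the same. The chi-square test is for counts. No survival method or censoring rule appears.
- **Incomplete data.** For the FAS, section 8.1 says that "the final measured efficacy data was used as end point data for analysis". The PPS keeps only patients who completed the efficacy evaluation. The abstract analyses efficacy in both sets.
- **Loss.** Section 4.3 foresees it: "The patients were lost, half-way to quit and other unpredictable problems". No rate is given.
- **Non-healing elsewhere.** Section 5.3 records "postoperative failure rate and related complications". Failure is not defined and is not in the section 6 list.
- **Imaging.** Section 13 and Appendix I (note 4) schedule X-ray and CT at 1, 2, 3, 4, 6 and 12 months after the operation.

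**The concern.** A t test needs one number per patient. Healing time has no number for a patient whose fracture has not healed when observation ends. A last-value rule works for a score measured at every visit, because an earlier score exists. It cannot work for a time to a single event, because before the event there is nothing of that kind to carry forward.

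Someone must then choose to drop these patients, assign them 12 months, or assign their last visit month. Dropping them removes any difference between arms in non-healing. Assigning 12 treats a lost patient as known to be unhealed. Assigning the last visit month treats a lost patient as healed on that day. The plan fixes none of these, so the choice can be made after the data are seen.

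**Working it through.** **1. Which patients have a value under the plan**

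| Patient | FAS | PPS |
|---|---|---|
| Seen to heal by month 12 | observed time | observed time |
| Lost before healing | last-value rule applies but has no healing time to use | removed (evaluation not completed) |
| Completes month 12 unhealed | no value | no value |

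**2. Figures in the plan.** There is no figure for healing time to reproduce. The sample size (40, 20 per arm) comes with no effect, SD, event rate or dropout rate. All rates below are assumptions.

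**3. Simulation set-up.** 20 per arm, 6,000 runs, two-sided 0.05 (the plan does not state sidedness).
- Healers' times are lognormal, median 4 months, log SD 0.3, recorded at the first of visits 1, 2, 3, 4, 6, 12 at or after healing.
- Lost patients' last visit is drawn uniformly from months 1, 2, 3, 4, 6, independently of healing.
- Log-rank: z = Σ(O − E)/√ΣV over visit months, with E = d·n₁/n and V = d(n₁/n)(1 − n₁/n)(n − d)/(n − 1). Here d is the number healed at the visit, n the number at risk, n₁ those at risk in one arm, and O those healed in that arm.
- Monte Carlo standard error is √(p(1 − p)/6000): about 0.3 points at 5% and 0.5 at 20%.

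**4. Non-healing differs, no loss** (% of trials with p < 0.05; here coding 12 and using the last visit month are the same)

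| Non-healing | t test, unhealed dropped | t test, coded 12 | Log-rank |
|---|---|---|---|
| 5% vs 5% | 4.7 | 4.7 | 4.9 |
| 5% vs 10% | 5.4 | 6.9 | 7.1 |
| 5% vs 20% (1 vs 4 of 20) | 4.3 | 16.3 | 20.2 |
| 5% vs 30% | 4.6 | 35.0 | 44.7 |

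Dropping unhealed patients leaves the rejection rate near 5% however large the difference.

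**5. Identical healing (5% non-healing in both arms), loss varies** (% false positives)

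| Loss | Dropped | Coded 12 | Last visit month | Log-rank |
|---|---|---|---|---|
| 10% vs 10% | 5.0 | 4.9 | not run | 5.1 |
| 5% vs 20% | 4.6 | 9.2 | 8.1 | 4.6 |
| 5% vs 25% (1 vs 5 of 20) | 4.4 | 12.0 | 9.4 | 4.7 |

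The last-visit column comes from a separate 4,000-run repeat; another repeat gave 9.7 at 5% vs 25%. Under smaller imbalances, coding 12 gives 5.4 (5% vs 10%) and 6.8 (5% vs 15%).

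**6. Direction of the bias.** In a second set-up (log SD 0.35, 4,000 runs, loss 5% vs 25%), the spurious mean difference was +0.76 month with 12 assigned, −0.59 with the last visit month, and −0.12 with healed patients only. The coding choice decides the sign.

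**7. Time origin.** Suppose months were counted exactly from discharge. A gap of D days in mean stay then shifts the comparison by D/30.44: 5 days gives 0.164 month and 10 days gives 0.329. With noncentrality shift/(SD·√(2/20)) and 38 df, false positives are 5.7% and 8.0% at SD 2, and 5.3% and 6.1% at SD 3.3. If healing is recorded as visit month after the operation, the shift is zero.

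**The case against.** **The false positives need a rule that the plan does not contain.** This stands. No section tells the analyst to assign 12 months or the last visit month. A reader might infer that the planned analysis itself has a 9–12% error rate, and the documents do not support that. A t test on observed healing times alone holds near 5% in every loss scenario in the table above; its fault is that it cannot see a difference in non-healing.

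**Lost patients are already handled.** This is partly right. A reader might infer that the plan says nothing about them, but the PPS removes them. The FAS has no workable rule for them, and neither set has one for patients who finish unhealed.

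**Non-healing is captured as failure.** This is partial cover at most. Failure is undefined and does not enter the healing-time comparison.

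**Expert guidance will settle it.** Sections 5.4 and 8.2 promise such guidance, but section 9.3 sends the database to the statistical experts after lock. No rule is fixed before then.

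**Healing time is not really counted from discharge.** A reader might infer from the abstract and section 6.2 that differences in hospital stay contaminate this outcome. The documents do not establish that. The discharge wording may only mark an observation window, as the VAS line in section 6.2 does ("first postoperative day to discharge day, maximum 2 weeks"), and imaging visits are counted from the operation. What remains is an ambiguity of wording.

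**The gain is modest.** This also stands: without loss, log-rank rejects in 20.2% against 16.3% for coding 12 at 5% versus 20% non-healing.

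**Conclusion.** The point holds as a gap in the analysis rule for one secondary outcome. That the last-value rule cannot supply a healing time follows from the text alone. The size of the harm depends on assumed rates. It is material if non-healing differs markedly and unhealed patients are dropped, or if loss is clearly unequal and lost patients are given a value. With equal or small loss and non-healing, the choice hardly matters.

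The log-rank figures assume that loss is unrelated to healing. The Rasmussen outcome is unaffected. The change should be made, at the low end of that priority.

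**What to change.** Add to section 8.2:

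> Fracture healing time is the time from surgery to the first scheduled imaging visit at which the healing criterion, stated in advance by the sponsor, is met. Patients not healed at their last imaging visit are censored at that visit; the last-value rule in 8.1 does not apply to this outcome. Arms are compared by Kaplan-Meier and log-rank on visit month, and the percentage healed at each visit is reported.

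As a minor edit, reconcile the discharge wording in the Project abstract and section 6.2 with the after-operation wording in section 5.1.

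**Cost.** This is wording plus one standard analysis on imaging already scheduled, with no extra visits or patients. Curves and percentages replace a simple mean. The gap between the 6- and 12-month visits makes late healing times coarse, and reporting the percentage healed by visit shows this openly. Power stays low with 40 patients.

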3.4 Study patients

Outpatient and emergency patients in trauma department of orthopedics of our hospital.

4. Research subjects

4.1 inclusion criteria

- (1) fresh closed fracture X-ray and CT examination diagnosed Schatzker type II-IV tibial plateau fracture patients
- (2) sign the informed consent form

- (3) age from 18 to 80 years

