8.2 Statistical analysis plan

There was no significant difference in age, gender, fracture type and other aspects between the two groups ($P>0.05$). Through epidemiological or statistical expert guidance, the experimental group and the control group data were analyzed using SPSS 22 statistical software, the measurement data in SX, using t test, count data expressed as a percentage, using X - test, $P < 0.05$, the difference has statistical significance, and draw the relevant charts with RevMan software.

9. Data management and statistical analysis

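### Postoperative collapse height is compared by an unadjusted t test, although starting height could be read from the preoperative CT that inclusion criterion 4.1 requires; adjusting for it is a cheap gain in precision, not the repair of an error

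*Combined protocol and SAP*

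**What the plan says.** **Endpoint.** Section 6.2 lists "Postoperative articular surface maximum collapse height (mm") as a secondary efficacy indicator. It is a postoperative value, not a change from the preoperative state. The abstract's outcome list does not include it. Section 5.3 places it in the follow-up after discharge ("maximal postoperative articular surface collapse height, postoperative failure rate and related complications") and names no analysis visit. Note 4 to the flow chart in Appendix I schedules X-ray and CT on the second day after surgery and at 1, 2, 3, 4, 6 and 12 months.

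**Analysis.** Section 8.2 says "the measurement data in SX, using t test, count data expressed as a percentage". Section 5.4 agrees: "using SPSS 22.0 statistical software analysis, measurement data to sx, using t test". The abstract gives the same method. No covariate, change score or model appears anywhere.

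**Baseline.** Section 4.1 admits patients with "fresh closed fracture X-ray and CT examination diagnosed Schatzker type II-IV tibial plateau fracture patients". However, the diagnostic criterion in the abstract and the screening step in section 5.2 let either X-ray or CT establish the fracture type. No section lists preoperative collapse height as a recorded item, and the flow chart's only screening entry on the fracture is its classification. On comparability, section 8.2 says only "There was no significant difference in age, gender, fracture type and other aspects between the two groups", with P>0.05. Allocation is by random table, with no stratification stated (5.2), to 20 patients per arm (3.3).

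**The concern.** Reduction of the joint surface is one of the two effects the trial sets out to compare (5.4), and Schatzker II-IV is a mixed population in which starting depth can be expected to vary. If residual height after surgery is related to starting depth, an unadjusted comparison leaves that explainable variation in the error term. In the one randomisation that occurs, a chance difference in starting depth between arms also passes in part into the observed difference.

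The comparability statement in 8.2 is no safeguard. It does not name collapse depth, and a non-significant baseline test in groups of 20 neither shows balance nor corrects imbalance. At stake are the width of the interval for this secondary endpoint and how a reader should interpret it if the arms happen to differ at the start.

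**Working it through.** **Plan's own figure.** The total of 40 has no power, effect size or SD behind it, so there is nothing to reproduce.

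**Inputs.** n = 20 per arm and N = 40 (3.3); P<0.05 (8.2), taken as two-sided because sidedness is not stated; all 40 patients analysed (assumed); r, the within-arm correlation of preoperative and postoperative height, is not in the documents and is assumed at 0, 0.3, 0.5 and 0.7.

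**Precision.** The raw difference has SE = SD × sqrt(2/20) = 0.316 SD. Adjusting for one baseline covariate multiplies the variance by

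V = (1 − r²) × [1 + 1/(N − 4)] = (1 − r²) × 37/36.

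The SE factor is sqrt(V) and the equivalent unadjusted total is 40/V. At r = 0.5, V = 0.75 × 1.028 = 0.771, sqrt(V) = 0.88 and 40/0.771 = 52.

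| Assumed r | V | SE factor | Equivalent total | Difference detectable at 80% power | Power at 0.8 SD |
|---|---|---|---|---|---|
| Raw t test | 1 | 1 | 40 | 0.91 SD | 69% |
| 0 | 1.03 | 1.01 | 39 | 0.92 SD | 68% |
| 0.3 | 0.94 | 0.97 | 43 | 0.88 SD | 72% |
| 0.5 | 0.77 | 0.88 | 52 | 0.80 SD | 80% |
| 0.7 | 0.52 | 0.72 | 76 | 0.66 SD | 93% |

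The last two columns use the noncentral t distribution, with 38 df for the raw test and 37 df after adjustment. The 0.8 SD difference is illustrative only.

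Break-even is where V = 1: r² = 1 − 36/37 = 1/37, so r = 0.16.

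**Adding Schatzker type.** Three types cost two more parameters. Charging three degrees of freedom in all, V = (1 − r²) × 38/35. At r = 0.3, 0.5 and 0.7 the SE factors are 0.99, 0.90 and 0.74, and the equivalent totals about 40, 49 and 72, if type explains nothing beyond height. In that case the gain at r = 0.3 all but vanishes.

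**Chance imbalance.** The difference in mean starting height between arms has SD sqrt(2/20) = 0.32 baseline SD. It exceeds 0.3 SD in 34% of randomisations and 0.5 SD in 11%. The raw outcome difference shifts by r × imbalance, so a 0.5 SD imbalance moves it by 0.15, 0.25 or 0.35 outcome SD at r = 0.3, 0.5 or 0.7. An imbalance of that size would normally pass a P>0.05 baseline check, which needs about 1.96 × 0.316 = 0.62 SD to be significant.

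**Type I error.** In 40,000 simulated null trials per value of r, the raw t test rejected in about 5% overall. Among the trials with an imbalance above 0.5 SD it rejected in about 8%, 13% and 21% at r = 0.3, 0.5 and 0.7.

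**Change score.** With equal SDs before and after surgery, its variance factor against the raw value is 2 − 2r, which falls below 1 only if r exceeds 0.5. A covariate-adjusted model is therefore the better choice.

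**The case against.** The strongest defence is that nothing here is wrong. A reader might infer that the t test is biased or that its P value cannot be trusted. The documents do not support that: under randomisation the test is unbiased with 5% type I error, and its standard error already allows for chance imbalance on average. The higher error rates above hold only conditionally on a large observed imbalance. This objection stands in full.

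Nor do the documents show that residual depth follows starting depth. Section 5.1 describes arthroscopic checking during the balloon procedure to avoid incomplete or excessive reduction. If both operations restore the surface almost fully, r could be small and the gain nil. This stands too, and is why the range starts at 0.

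A reader might also infer that preoperative collapse is already measured, because 6.2 lists recovered area as a percentage of collapse area. That wording is unclear, concerns area and does not show that depth in mm is recorded. If it is read as scaled to each patient's initial collapse, it works the other way: the plan then has one reduction outcome that already allows for starting severity.

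That every patient will have a preoperative CT follows from 4.1, but it sits beside the X-ray or CT wording in the abstract and 5.2. Finally, the endpoint is secondary and absent from the abstract's list, so no primary conclusion depends on it.

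What survives is that 4.1 provides for the scan, the analysis ignores it, and using it costs little.

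**Conclusion.** The point holds as a cheap improvement to a secondary analysis. The unadjusted t test is valid but gives up precision if r is above about 0.16, and it makes no correction if the arms happen to differ in starting depth. The size depends entirely on r: from a trivial loss at r = 0 (SE up by about 1%) to an SE about 28% smaller at r = 0.7, with 40 patients doing the work of about 39 to 76.

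A reader might take 40/(1 − r²), that is 44, 53 and 78 at r = 0.3, 0.5 and 0.7, as the gain. That shortcut leaves out the cost of estimating the covariate; 43, 52 and 76 are the figures to use.

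The result assumes 20 analysed patients per arm, a linear relation with a common slope in both arms, and a preoperative CT for every patient as in 4.1.

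**What to change.** 1. Reconcile the X-ray or CT wording (diagnostic criterion in the abstract; screening step in 5.2) with the X-ray and CT wording (inclusion criteria in the abstract and 4.1).
2. Add preoperative maximum collapse height (mm) to the CRF, read from the entry CT by the same method as the postoperative value.
3. Name one scheduled postoperative CT as the analysis time point for this endpoint. Without it the outcome variable is undefined, whichever test is used.
4. In 8.2, prespecify, before outcomes are compared by arm, a linear model for postoperative height with arm and preoperative height. Report the adjusted mean difference with its 95% CI and keep the t test as supportive. Schatzker type is optional, because it costs two more degrees of freedom.

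The cost is one extra reading per existing scan, one CRF field and a sentence or two in 8.2. The only statistical downside is the roughly 1% wider standard error if the correlation is near zero.
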